1.3 HCV among men who have sex with men

New HCV infections are typically found in HIV-positive MSM. Incidence of initial infection among HIV-positive MSM stabilized and was not markedly declining before DAA became widely available.(14-16) Since unrestricted DAA availability in November 2015, HCV incidence has been decreasing in the Netherlands.(17, 18) The incidence rate of acute HCV infection among HIV coinfected MSM in HIV care was 4.5 diagnoses per 1,000 PY in 2012,

6.6 in 2015 and 3.3 in 2017.(18) International data show diverging trends. In Switzerland and France for example, HCV incidence in MSM has remained stable or has shown an increase respectively(19, 20), since the availability of DAA's.

Of great concern is the more than ten times higher risk of reinfection when compared to initial infection; approximately one third of the MSM who successfully responded to HCV treatment acquired a reinfection within 2 years.(21, 22) A subsequent high incidence of HCV reinfection has also been observed in other high income countries in MSM who both respond to treatment or clear the infection spontaneously.(23, 24) An additional concern is the recent finding of a higher HCV prevalence (4.8%) in high risk HIV-negative MSM than previously reported.(25) These HCV mono-infected MSM applied for pre-exposure prophylaxis (PrEP) to prevent HIV infection and were infected with HCV strains already circulating among HIV-positive MSM. More recent data shows that the HCV incidence rate in HIV negative MSM on PrEP comparable is to that of HIV-positive MSM.(20, 26) Increasingly overlapping sexual networks between HIV-positive and HIV negative MSM(27, 28) might put these HIV-negative MSM also at risk of HCV reinfection and spread to the larger population of HIV-negative MSM cannot be excluded.

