7.1.2 Secondary study parameters/endpoints

1. Incidence rate of HCV reinfection (number of cases of HCV reinfection divided by total person-years of follow-up at risk for reinfection) (self-reported and laboratory data).
2. Incidence rate of any STI (number of cases of chlamydia, gonorrhoea, lymphogranuloma venereum (LGV), genital herpes and/or syphilis divided by total person-years) (self-reported).
3. Changes in HCV-related risk behaviour:
 - a. Changes in the number of sex partners.
 - b. Changes in the number of condomless anal sex acts with casual partners.
 - c. Changes in the individual items of the HCV-MOSAIC risk score:
 - i. Changes in the proportion of individuals reporting receptive condomless anal sex.
 - ii. Changes in the proportion of individuals sharing sex toys.
 - iii. Changes in the proportion of individuals reporting unprotected fisting.
 - iv. Changes in the proportion of individuals reporting injection drug use.

- v. Changes in the proportion of individuals sharing snoring equipment during nasally-administered drug use.
- vi. Changes in the proportion of individuals reporting ulcerative sexually transmitted infection (syphilis, genital herpes or lymphogranuloma venereum infection).
- d. Proportion of individuals with change in any of the items of the HCV-MOSAIC risk score.
- e. Changes in the frequency of recreational drug use before and during sex.
- f. Changes in the frequency of individuals engaging in group sex activities, including changes in number of events and maximum number of sex partners during an event.
- g. Changes in the proportion of individuals sharing lubricants.
- h. Changes in the proportion of individuals sharing anal douches.

4. Changes in the proportion of individuals disinfecting sex toys, skin and/or sex location.
5. Changes in the sexual wellbeing score.

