- Data on the number of free HCV home-based test(s) used and their test results will be collected from Castor EDC platform if assigned to intervention II or III.
- Data on HCV reinfection (HCV RNA test date(s), test results and HCV treatment) will be collected from laboratory and clinical files of the participating sites, and the Dutch HIV monitoring foundation (in Dutch: Stichting HIV Monitoring, SHM):
 - HIV treatment center: only for HIV-positive participants. Linkage will be performed using study number if the participant provided consent via the informed consent form. Linkage to SHM data will be through the HIV treatment centers using routine procedures.
 - STI/PrEP/sexual health center: for HIV-negative participants and HIV-positive participants (HIV-positive patients also visit the STI outpatient clinic at the Public Health Center of Amsterdam). Linkage will be performed using name and date of birth to link the STI data.
- Additional HCV RNA blood testing will retrospectively be performed to test for HCV reinfection if: 1) the participant did not receive HCV RNA testing in the 6 months prior to the end of the study period, 2) there is a blood sample available for HCV RNA testing at the laboratory of the participating site and 3) the participant provided consent for retrospective HCV RNA testing in the informed consent form. These blood samples are routinely collected during visits at the HIV treatment center or at the STI/PrEP/sexual health center every 3-6 months (see **Chapter 7.3**) and are retained at the laboratory for a minimum of 2 years according to law.

The data manager at the Public Health Service of Amsterdam will import the data from the questionnaires, the behavioural intervention, Castor EDC, HCV test results and clinical data into the Research SQL database (database 2).

The data of the participants will be stored in two separate databases: 1) containing study number and directly identifiable personal data (subject identification code list) and 2) containing study number and study data (e.g., sexual risk behaviour data). The subject

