2.1.2. Secondary endpoints

- **Definition**

Secondary endpoints are as follows:

- Incidence rate of HCV reinfections during both the run-in (i.e., M0 and M6) and intervention period (i.e., M12, M18, M24), both self-reported and laboratory-confirmed, defined as the number of cases divided by the total person-years of follow-up at risk for reinfection
- Incidence rate of any STI during the run-in and intervention period, both self-reported and laboratory-confirmed, defined as the number of chlamydia, gonorrhoea, genital herpes and/or syphilis infections divided by the total person-years of follow-up
- Other HCV-related risk behaviour during run-in versus intervention period, more specifically:
 - Changes in the mean or median number of sex partners (depending on the distribution of the variable of interest)
 - Changes in the mean or median number of condomless anal sex acts with casual partners (depending on the distribution of the variable of interest)
 - Changes in the proportion of participants reporting any individual behaviours that are included in the HCV-MOSAIC risk score
 - Changes in mean or median sexual wellbeing score (depending on the distribution of the variable of interest)
- The proportion of participants achieving an HCV-MOSAIC risk score ≥ 2.0 at the end of follow-up compared between intervention arms (in both ITT and PP populations)

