2.2.2. Comparative analysis

The primary endpoint is compared between the run-in period (i.e., at M0, M6) and at each time point during the intervention period (i.e., at M12, M18, M24) using a mixed-effect logistic regression model. In this model, each individual serves as their own control and between-individual differences at baseline are accounted for using a random-intercept. Odd ratios (OR) comparing the odds of run-in versus intervention time points, along with their 95% confidence intervals (CI), are estimated and stratified on study arm. These stratified analysis are performed by including an interaction term between arm and study time point (along with their individual covariate) in the model, while study time points are statistically tested within strata of the study arms. Comparisons between run-in and intervention time points are systematically conducted as follows:

- Unadjusted;
- Adjusted on the randomisation strata (country and, if sufficient numbers of individuals in each intervention arm are available, inclusion centre [3]);
- Adjusted on covariates that could potentially affect the evaluation of the primary outcome

Incidence rates of HCV reinfections and STIs are calculated during the run-in and interventions periods, separately. Considering that few HCV reinfections are likely to occur,

we intend to analyse the relative difference in incidence rates between periods using a Bayesian exponential survival regression model with non to weakly informative *a priori* distributions [4, 5]. The relative difference in incidence rates of STIs are compared between periods using a Poisson regression model with ln of person years of observation as an offset. These models are run on both the overall study population and stratified by treatment arm (using the same model configuration of fixed-effect covariates as in the primary endpoint).

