2.3. CALCULATION CONVENTIONS

2.3.1. Convention for defining follow-up time

- Follow-up during the run-period is defined as the amount of participation time for each participant enrolled from moment of inclusion (following sign inform consent) until the moment of randomisation
- Follow-up during the intervention period is defined as the amount of participation time for each participant enrolled from moment of randomisation until last study visit

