2.3.2. Convention for time calculations

- Time between two dates in months or years is estimated as the number of months between two dates by subtracting the later date to the earlier date
- Calculation of age in years at enrolment =
$$\frac{\text{date of enrollment} - \text{date of birth}}{365.25}$$
- Date of HCV reinfection is estimated using the mid-date between the last HCV-RNA negative and first HCV-RNA positive test result
- Calculated time at risk for HCV risk is defined as the amount of participation time for each participant enrolled from moment of inclusion until estimated date of HCV reinfection or the last recorded HCV-RNA negative test date

- STI period prevalence is estimated using the proportion of participants that have a positive STI test result (self-reported) at any study visit during the past 6 months

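### The SAP's time-at-risk rule for HCV reinfection has no return to risk after cure, which can lower the intervention-period rate without any intervention effect

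*SAP*

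**What the plan says.** SAP 2.3.2 sets time at risk for HCV as one interval per participant: "from moment of inclusion until estimated date of HCV reinfection or the last recorded HCV-RNA negative test date". The reinfection date is the midpoint between the last negative and first positive RNA result. Neither document says what happens to a man's time or events after that date.

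The rate itself is not limited to first events. SAP 2.1.2 has it "defined as the number of cases divided by the total person-years of follow-up at risk for reinfection", and Protocol 7.1.2 similarly has "number of cases of HCV reinfection divided by total person-years of follow-up at risk for reinfection".

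The comparison is before versus after. SAP 2.2.2 states that "Incidence rates of HCV reinfections and STIs are calculated during the run-in and interventions periods, separately", and then that "we intend to analyse the relative difference in incidence rates between periods using a Bayesian exponential survival regression model", overall and by arm. It states no participant-level term for this model, whereas the behavioural outcomes get a random intercept.

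Follow-up does not stop at reinfection: SAP 2.3.1 runs the intervention period "from moment of randomisation until last study visit". Current HCV infection is an exclusion at enrolment only (Protocol 4.3), and no rule withdraws a man reinfected during the run-in.

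**The concern.** Every participant has already been cured of HCV or has cleared it, so renewed risk after cure is the premise of the trial. A single interval that ends at reinfection does not reflect that premise.

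Two problems follow from a literal reading. First, numerator and denominator do not match: a second reinfection is a case under the rate definition but has no time at risk behind it. Second, men reinfected early are, on average, at higher risk than those who are not. The run-in always comes first and starts with everyone at risk; the intervention period starts without the run-in cases and keeps losing higher-risk men. The later rate then drifts down whether or not the interventions work. There is no concurrent untreated arm to show the same drift, so it could be taken for an intervention effect on the reinfection endpoint.

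**Working it through.** The documents give no expected reinfection rate, event count or power for this endpoint, so there is no stated figure to reproduce. The check asks what ratio the literal rule yields when the interventions do nothing.

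**Inputs from the documents**
- 246 enrolled (Protocol 4.4, SAP 1.4); run-in 0.5 year, intervention 1.5 years (SAP 1.2.1).
- High case: Protocol 1.3 says "approximately one third of the MSM who successfully responded to HCV treatment acquired a reinfection within 2 years".
- Lower cases: Protocol 1.3 gives 3.3 (2017) and 6.6 (2015) acute diagnoses per 1,000 person-years and a reinfection risk more than ten times that of initial infection. Taking exactly ten (an assumption): 10 × 3.3/1,000 = 0.033 and 10 × 6.6/1,000 = 0.066 per person-year.
- Risk differs between men: Protocol 9.1 reports an AUC of 0.76 for the HCV-MOSAIC score against reinfection.

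**Assumptions**
- Each man has a constant hazard; hazards vary between men as a gamma frailty with mean 1 and variance θ.
- To size θ, assume normally distributed log-risk: SD = √2 × Φ⁻¹(0.76) = 1.00, so the variance of relative risk is exp(1.00²) − 1 ≈ 1.7. Other values are shown below.
- Complete follow-up, exact dating of infection, and everyone continuing into the intervention period.

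**Formulas**
- Probability of no reinfection by time t: S(t) = (1 + θλt)^(−1/θ), with λ the mean hazard. In the high case λ is solved so that 1 − S(2) = 1/3, giving λ = 0.292 at θ = 1.7.
- Run-in rate = [1 − S(0.5)] / ∫S from 0 to 0.5.
- Intervention rate = [S(0.5) − S(2)] / ∫S from 0.5 to 2.
- SE of the log ratio = √(1/run-in events + 1/intervention events), pooled over arms.

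**Results, θ = 1.7, no intervention effect** (rates from unrounded values)

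| Case | Run-in events / PY | Intervention events / PY | Rates per 100 PY | Ratio | SE of log ratio |
|---|---|---|---|---|---|
| 0.033 per PY | 4.0 / 122.0 | 10.9 / 354.7 | 3.25 vs 3.09 | 0.95 | 0.59 |
| 0.066 per PY | 7.8 / 121.0 | 19.8 / 341.9 | 6.42 vs 5.80 | 0.90 | 0.42 |
| One third in 2 years | 30.1 / 115.0 | 51.9 / 280.2 | 26.13 vs 18.54 | 0.71 | 0.23 |

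In the first two cases the distortion is well inside sampling error (|ln 0.90|/0.42 ≈ 0.25 SE). In the third it is about 1.5 SE (|ln 0.71|/0.23).

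**Sensitivity to θ.** Over θ = 0.5 to 3 the ratio runs from 0.98 to 0.91, 0.97 to 0.85 and 0.91 to 0.54 in the three cases. At θ = 0 (equal risk) it is exactly 1.00 in each.

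**How much comes from run-in cases.** The hazard among men still at risk at month 6 is λ/(1 + θλ/2). In the high case this is 0.292/1.248 = 0.234; against the run-in rate of 0.261 the ratio is about 0.89. On the log scale that is about a third of the fall to 0.71. At 0.066 per PY the corresponding figure is 0.97, a smaller share. The rest is continued depletion after randomisation.

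**With re-entry** (simulated, 2,000,000 men per scenario, θ = 1.7). Cases are in the same order as the table.

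| Time out of risk after each reinfection (assumed) | Ratio in the three cases |
|---|---|
| None | 1.00, 1.00, 1.00 |
| 0.25 year | 1.00, 0.99, 0.98 |
| 0.5 year | 0.99, 0.98, 0.93 |

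A long gap leaves more behind. With one third reinfected and θ = 2, the ratio is 0.67 without re-entry, 0.93 with a 0.5-year gap and about 0.81 with a 1-year gap.

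**The case against.** A reader might infer that the SAP deliberately restricts the analysis to first reinfections and removes men for good. It does not say so. That is the literal result of a text silent on re-entry, and the rate definitions, which count cases without restriction, point the other way. The convention also does not say which end date applies to a man who has both a reinfection and a later negative test. This objection narrows the point but does not remove it: an analyst following 2.3.2 as written has no basis for restarting the clock.

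A reader might also infer that the ratio must fall in every arm. It need not: the fall requires unequal risk. The high case may also be too pessimistic. Protocol 1.3 reports falling incidence of acute infection, and both documents expect few reinfections. Pushing the variance to 4 with one third reinfected gives 0.44, but implies about 40 run-in reinfections among 246 men, which does not fit that expectation.

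The net direction is not settled either. Protocol 7.3 describes some centres testing annually or only when liver enzymes are raised. Two arms then receive four home tests, and stored samples may be tested after the end of the study. More detection later could raise the intervention-period rate and offset the depletion.

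Finally, time to first event is a conventional choice, a viraemic or treated man is rightly out of the risk set, and this is a secondary endpoint in a study described as a pilot. All of this stands and limits the weight of the point. It does not justify leaving numerator and denominator unmatched.

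**Conclusion.** The point holds as a defect in the stated time-at-risk rule, with a conditional and probably modest effect. Under a literal reading and no intervention effect, the intervention/run-in ratio is about 0.95 to 0.90 at 0.033 to 0.066 per person-year, about 0.71 at one third in 2 years, and 1.00 if all men share the same risk. The frailty variance of 1.7, the exact tenfold multiplier and complete detection are assumptions.

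The documents do not support saying that the plan will produce a false intervention effect, or that losing the run-in cases accounts for most of the fall. At the event numbers expected, the distortion could not be told from chance, and changes in testing may move the ratio the other way. The HCV-MOSAIC primary comparison is unaffected. Comparisons between arms should be less affected, because depletion before randomisation is balanced in expectation. The change should still be made: it is cheap, and with so few events repeat reinfections should not be lost or left without person-time.

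**What to change.** In SAP 2.3.2:
- stop time at risk at the estimated reinfection date and restart it at the first HCV-RNA negative result showing cure or clearance;
- split each man's person-time at randomisation;
- count every reinfection in the period in which it occurs, so that cases and person-time match.

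In SAP 2.2.2, allow for within-person correlation in the Bayesian exponential model, for example with a participant-level term under a weakly informative prior. Keep a first-reinfection analysis, with only first events in the numerator, as a sensitivity analysis, and report how many men leave the risk set during the run-in.

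The cost is SAP wording and a recurrent-event data layout. No new data are needed for the restart date: under Protocol 11.1, "Data on HCV reinfection (HCV RNA test date(s), test results and HCV treatment) will be collected". There are three downsides. A prespecified data rule is needed to separate reinfection from relapse. A participant-level term will be weakly identified with few events, so the prior should be stated. Where negative tests come late, re-entry reduces the distortion without removing it, so the gap between reinfection date and restart should be reported by period and arm.

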2.3.3. Convention for HCV-MOSAIC risk score calculations

The HCV-MOSAIC risk score consists of six self-reported risk behaviours and is calculated by summing the beta coefficients of the following factors, when present:

- Condom less receptive anal intercourse ($\beta = 1.1$)
- Sharing of sex toys ($\beta = 1.2$)
- Unprotected fisting ($\beta = 0.9$)
- Injecting drug use ($\beta = 1.4$)
- Sharing of straws during nasally-administered drug use ($\beta = 1.0$)
- Having an ulcerative STI ($\beta = 1.4$)

A score of 2.0 or higher indicates that the person is at risk of HCV infection.

2.3.4. Other calculation conventions

- Categorical variables:
 - Age in years: <35, 35-44, ≥ 45
 - Ethnicity: Dutch, French, Other
 - Educational level: low, middle, high
 - HIV status: with HIV, without HIV
 - PrEP use: no PrEP use, daily prep use, event-driven prep use

2.4. SOFTWARE

Analyses are performed using STATA Intercooled software (version 15.0 or higher) and R software (version 4.0.0 or higher) if it is impossible to perform certain analysis or produce figures with STATA.

3. ANALYSIS PLAN

3.1. DESCRIPTION OF ENROLMENT AND FOLLOW-UP

Treating physicians and nurses at the study centres propose the study to individuals meeting study inclusion criteria. Only until verbal and written informed consent is obtained are individuals enrolled in the study. Only one site visit is required at the start of the study (i.e., to sign informed consent), all further study procedures take place online or at home. Participants are invited to complete the study questionnaire every six months by email (five in total).

3.1.1. Flowchart

According to the CONSORT diagram [6]:

- Participants assessed for eligibility (n)
- Participants assessed for eligibility and not enrolled (n, %) – the denominator of the proportion is the number of participants assessed for eligibility
- Participants enrolled (n, %) – the denominator of the proportion is the number of participants assessed for eligibility
- Participants having completed the baseline study visit (n, %) – the denominator of the proportion is the number of participants enrolled
- Participants reaching M6 and were randomised (n, %) – the denominator of the proportion is the number of participants enrolled
- Participants having completed all study visits (n, %) – the denominator of the proportion is the number of participants randomized
- Withdrawals (n, %) – the denominator of the proportion is the number of participants enrolled

3.1.2. Description of pre-enrolments

- Participants assessed for eligibility in total, per country and per centre (n)
- Participants assessed for eligibility and non-enrolled in total, per country and per centre (n, %) – the denominator of the proportion is the number of participants assessed for eligibility

3.1.3. Description of enrolment

- Participants enrolled in total, per country and per centre (n, %) – the denominator of the proportion is the number of participants assessed for eligibility
- Enrolment graph (i.e., the number of participants enrolled from first until last enrolment)
- Monthly enrolment graph (i.e., the number of participants enrolled per month)

3.1.4. Description of follow-up

- Expected visits corresponding to the number of participants enrolled (n)
- Visits actually conducted over the number of expected visits (n, %) – the denominator of the proportion is the number of expected visits corresponding to the number of participants enrolled

3.1.5. Early trial discontinuation

- Participant withdrawals (after enrolment) (n, %) – the denominator of the proportion is the number of participants enrolled
- Reasons for withdrawal (after enrolment) (n, %) – the denominator of the proportion is the number of withdrawals after enrolment
- Last visit before discontinuation (n, %) – the denominator of the proportion is the number of withdrawals after enrolment
- Time between enrolment date and date of early discontinuation during the run-in period (in months) for those who withdrew
- Time between randomisation date and date of early trial discontinuation (in months) for those who withdrew

